13.5.3.2 Secondary Effectiveness Analysis

The null hypothesis of no difference between treatment groups in ECD loss will be tested for the ITT set using the multiple imputation method and statistical model described above for the primary effectiveness analysis. A two-sided 95% confidence interval will be constructed around the difference between groups. If the null hypothesis is rejected then statistical superiority will be claimed for the test OVD in this endpoint.

13.5.4 Surgery Data

The surgery data described in [Appendix C](#) will be summarized descriptively. Any planned analyses of surgery data will be detailed in the study SAP.

13.5.5 Patient Disposition

Enrollment status will be summarized in a table by investigator and overall for the all enrolled set. The number and percentage of enrolled eyes will be summarized as well as the number and percentage of eyes that completed the entire trial, discontinued before surgery, and discontinued after surgery. In addition, for those eyes that did not complete the entire trial, the reason for discontinuation will be summarized.

Subject accountability at each form visit will be summarized for all enrolled subjects in a table. The subject accountability table will also be stratified by investigator and by treatment assignment.

Subjects in the Safety, ITT, and PP Populations will be summarized categorically by treatment and overall.

13.5.6 Demographics and Baseline Characteristics

Race, gender, ethnicity, and age and will be presented using discrete summary statistics by treatment group. Age will also be presented using continuous summary statistics by treatment group.

13.5.7 Protocol Deviations

The number of subjects within each type of protocol deviation will be presented using discrete summary statistics.

Major protocol deviations leading to exclusion from the PP Set will include the following.

- Ineligibility
- Use of an incorrect OVD including misrandomized subjects
- Disallowed concomitant treatments including IOP lowering treatments
- Missing IOP value at postoperative visit 1 or 2

Additional major protocol deviations may be identified prior to unmasking of the treatment assignments.

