13.4.3 Per Protocol Population

The Per Protocol (PP) Population will include all randomized eyes without major protocol deviations. Protocol deviations resulting in exclusion from the PP Set are described in Section 13.5.7.

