13.5.2 Primary Effectiveness Analysis

Specular microscopy of the central cornea will be completed preoperatively and at Visit 5 (90 ± 14 days postop). Images will be evaluated by a masked reading center. If multiple cell densities are obtained from the reading center for each eye visit, then the available counts will be averaged by eye and visit (Preoperative, Visit 5) to produce a single value for each eye visit.

If one or more ITT Population eyes has a missing mean ECD value either at the preoperative visit or at Visit 5 (including due to a missed visit or due to discontinuation), then the missing data will be imputed as follows. Prior to analysis, 25 imputations of missing mean densities will be produced using the Markov chain Monte Carlo method and the variables investigator, treatment, preoperative value, and postoperative value.

For each observation in the imputed datasets, the ECD loss in percent at Visit 5 will be calculated for each eye at each visit as follows:

$$\text{Loss (\%)} = \frac{\text{Preoperative Cell Density} - \text{Visit 5 Cell Density}}{\text{Preoperative Cell Density}} \times 100\%$$

The means and standard errors from the imputed datasets will be combined to produce a continuous variable summary of the ECD (cells / mm^2) at each visit (Preoperative, Visit 5) and the percent loss at Visit 5 by randomized treatment assignment for the ITT Population.

Loss (%) will be modeled as a function of the fixed class variables treatment and investigator, separately by imputation. The parameter estimates will be combined to produce a one-sided upper 95% confidence limit for the difference in percent loss between the test

and comparator OVDs and a p-value for the hypothesis test for the ITT Population. If the upper confidence limit is less than 5%, then the null hypothesis of inferiority will be rejected in favor of the alternative hypothesis of non-inferiority.

If there are no ITT Population eyes with missing ECD data, then imputation will not be performed. Instead, the available data will be analyzed and summarized as described above.

Sensitivity analyses of effectiveness will include a best-case analysis, a worst-case analysis, a tipping point analysis, and a complete case analysis (which will use only subjects who have cell density measurements at every scheduled visit), and analysis using the PP Set.

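### The single Per Protocol set drops eyes with valid cell counts from the ECD sensitivity analysis for a missing early IOP, and has no criterion for an out-of-window Visit 5 count

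*Combined protocol and SAP*

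**What the plan says.** Section 13.4.3 defines one PP population for all purposes. It "will include all randomized eyes without major protocol deviations", and the reader is sent to Section 13.5.7 for what counts as major. That section lists four items:

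- "Ineligibility"
- "Use of an incorrect OVD including misrandomized subjects"
- "Disallowed concomitant treatments including IOP lowering treatments"
- "Missing IOP value at postoperative visit 1 or 2"

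It adds an open clause: "Additional major protocol deviations may be identified prior to unmasking of the treatment assignments".

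The set is used for both primary endpoints. Section 13.5.1 repeats the IOP analysis in it, on observed data only. Section 13.5.2 ends its list of ECD sensitivity analyses with "and analysis using the PP Set" and does not say whether that analysis uses observed or imputed data.

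Sections 9.3.2 and 9.3.4 also bear on membership. The first removes from PP the subjects given an IOP-lowering drug during surgery. The second removes those treated for an IOP below 30 mmHg.

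**The concern.** The ECD endpoint rests on two measurements, the preoperative count and the Visit 5 count. A PP set for that endpoint should keep eyes in which both were obtained as planned after the assigned device was used, and remove eyes in which they were not. The listed criteria miss this in two ways.

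First, an eye with two good counts is lost because a 6-hour or 24-hour pressure was not recorded. Second, a Visit 5 count well outside its window stays in, because nothing on the list refers to it.

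IOP-lowering treatment raises a separate issue. It follows randomization and may reflect how the OVD behaved, so excluding on it makes membership of the ECD comparison depend on something related to the other primary endpoint.

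At stake is whether the PP analysis can do its job beside the ITT result: show that non-inferiority on ECD also holds among eyes that followed the protocol in the respects that matter for ECD.

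**Working it through.** **Criteria set against the ECD endpoint**

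| Item in 13.5.7 | Bearing on the two cell counts |
|---|---|
| Ineligibility | Yes, at baseline: Section 8.2 excludes a baseline ECD below 1500 cells/mm² and eyes where specular microscopy is unreliable |
| Incorrect OVD | Yes: it defines the exposure |
| IOP-lowering treatment | Indirect at most, and after randomization |
| Missing IOP at Visit 1 or 2 | None |
| Visit 5 count outside 90 ± 14 days | Not listed |

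The last row has a practical consequence. Under Section 11.1.4, a visit meant to serve as a scheduled visit but made outside its range is still entered on that scheduled visit's form. Section 11.1.5 calls a visit missed once the next visit's range opens, and no scheduled visit follows Visit 5. A late count therefore enters as Visit 5 data, and no listed PP criterion removes it.

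**The plan's own power figure**

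Inputs from Section 13.3.2: n = 165 per arm, margin 5 points, SD 14.2, true difference 0, one-sided alpha 0.05.

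λ = 5 / (14.2 × √(2/n)); power = P(noncentral t with 2n − 2 df and parameter λ exceeds t at 0.95).

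For n = 165: 14.2 × √(2/165) = 1.563; λ = 3.198; critical value 1.650; power 0.9390. The stated 93.90% reproduces.

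**Loss of eyes**

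The documents give no rate for a missing Visit 1 or 2 IOP, so 5% is assumed. The planning incidence of IOP at or above 30 mmHg is 0.117 (Section 13.3.1). Counts are rounded down, the two exclusions are taken as independent, and the dropped eyes are assumed otherwise evaluable for ECD.

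| Case | Eyes per arm | Power |
|---|---|---|
| No IOP-based exclusion | 165 | 93.90% |
| 5% missing early IOP | 165 × 0.95 = 156 | 92.76% (λ = 3.110) |
| 11.7% excluded for IOP-lowering treatment | 165 × 0.883 = 145 | 91.09% (λ = 2.998) |
| Both | 165 × 0.883 × 0.95 = 138 | 89.85% (λ = 2.925) |

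The last two rows require that every eye reaching 30 mmHg is treated and that this treatment counts as an exclusion.

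**Does that treatment count?**

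Section 9.3.4 attaches the PP exclusion to treatment below 30 mmHg, and Section 9.3.2 to intraoperative use. At 30 mmHg or above, Section 9.3.4 itself directs the investigator to treat. Section 13.5.7 speaks of disallowed treatments and includes IOP-lowering treatments without a threshold. The text supports either reading, and the number of ECD eyes lost depends on which is meant.

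**The case against.** The strongest reply is that little depends on this analysis. The primary ECD analysis is ITT with multiple imputation, and Section 13.7.3 ties success to the primary analysis populations. PP is one of five ECD sensitivity analyses, with best-case, worst-case, tipping-point and complete-case. The complete-case analysis already uses every eye with both counts, with no IOP criterion. One subject-level PP set is common practice, and the open clause in 13.5.7 could add a Visit 5 criterion before unmasking.

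The point about weight stands and limits the finding. The rest does not remove it. The open clause can add exclusions but not lift the missing-IOP exclusion, and an unspecified later addition is not prespecified. The complete-case analysis is not a protocol-adherent set: it does not remove ineligible eyes or eyes given the wrong OVD.

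A reader might infer four stronger things that the documents do not support:

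- **That the PP result is the main support for non-inferiority on ECD.** No decision rule uses it.
- **That about 43 eyes (0.117 × 368) will be dropped for treated pressure spikes.** This needs the wide reading of 13.5.7, which 9.3.2 and 9.3.4 do not share.
- **That the PP analysis is biased toward non-inferiority.** This needs treated eyes to lose more cells and to be more frequent on test. Nothing in the documents shows either. Section 5 says a highly dispersive OVD coats better but is harder to remove, so higher pressure could accompany better protection.
- **That no PP criterion concerns ECD.** Ineligibility covers baseline ECD; only Visit 5 is uncovered.

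It is also fair to say that some IOP-lowering measures may not be irrelevant to the endothelium. Section 9.3.2 gives surgical complication as the example for intraoperative use, and 9.3.4 lists fluid release through the corneal incision. The claim of no bearing on the count is therefore confined to the missing-IOP criterion.

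**Conclusion.** The point holds for the ECD sensitivity analysis in the PP set and goes no further; the primary ECD conclusion is unchanged. As written, the plan drops eyes with complete ECD for a missing 6-hour or 24-hour IOP and keeps Visit 5 counts taken out of window. It also applies an IOP-lowering exclusion whose scope its own sections do not agree on.

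The loss of precision is small: about 1.1 points of power (93.90% to 92.76%) under the assumed 5% missing early IOP. It reaches about 4 points (to 89.85%) only under the wide reading combined with the 11.7% planning rate. Selection on a post-randomization event is possible, but neither its direction nor its size can be determined from the documents. The change is worth making because the rule is wrong for this endpoint and costs almost nothing to correct before database lock.

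**What to change.** Keep the current list for the IOP PP analysis. In 13.4.3 and 13.5.7, define a second flag, PP-ECD, and use it in 13.5.2:

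- Exclude ineligible eyes, eyes given an incorrect OVD, and eyes whose Visit 5 ECD is missing or outside 90 ± 14 days.
- Do not exclude for a missing IOP at Visit 1 or 2.
- State that the analysis uses observed data only. Section 13.5.1 already says this for IOP; 13.5.2 is silent, and the no-imputation default in 13.7.1 is open to change in the SAP.

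Reconcile the wording of the IOP-lowering exclusion across 9.3.2, 9.3.4 and 13.5.7. State in each place that it governs the IOP PP set and not PP-ECD; otherwise 9.3.2 and 9.3.4 would contradict the new flag. Because 13.4.4 builds the Best Case Population on PP, say there which flag it starts from.

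The cost is one more population flag and a few lines of text, with no new data. Section 13 has the SAP approved before database lock, so there is a natural place for the change.

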13.6 Interim Analyses

No interim analyses are planned.

13.7 Additional Statistical Considerations

13.7.1 Handling of Missing Data

Imputation of missing primary endpoint data is described in Section 13.3 above. Unless otherwise specified in the SAP, missing data will not be imputed.

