13.5.1 Primary Safety Analysis

IOP will be assessed in the study eye using Goldmann tonometry at each scheduled follow-up visit and may be assessed at unscheduled visits.

Subjects with $IOP \geq 30$ mmHg at any follow-up visit ($IOP \geq 30$ mmHg at any follow-up visit, No $IOP \geq 30$ mmHg at any follow-up visit) will be summarized using categorical summary statistics for the Safety Population by actual treatment received in a table. Missing data will not be imputed for this summary table.

Missing IOP values will be imputed using Markov chain Monte Carlo (MCMC) methods. Twenty imputed datasets will be produced using a seed of 1017144149. The variables used in the imputation model will include IOP at baseline and at each of the scheduled postoperative visits. After missing data at scheduled visits has been imputed, unscheduled visit IOP values will be added to each imputed dataset.

Within each imputed dataset, subjects will be classified as belonging to one of the following groups:

- $IOP \geq 30$ mmHg at any follow-up visit
- No $IOP \geq 30$ mmHg at any follow-up visit

This classification will be based on experiencing at least one IOP measurement of 30 mmHg or more at any follow up visit over the entire course of the study. Subjects experiencing one or more IOP spikes will be counted only once.

The difference between test and control in the proportion of subjects with $IOP \geq 30$ mmHg at any follow-up visit and the asymptotic standard error will be estimated separately for each imputation.

An estimated difference between treatment groups and a two-sided asymptotic Wald 95% confidence interval around the difference will be constructed via combination of the proportion differences and standard errors from the imputations. If all the imputations result in the same estimated difference and confidence interval, then the results of a single imputation may be used.

If the upper confidence limit (equivalent to a one-sided upper 95% confidence limit) is less than 0.117 (11.7%), then the null hypothesis of inferiority will be rejected in favor of the alternative hypothesis of non-inferiority. A p-value will also be provided for this one-sided hypothesis test.

The primary safety analysis will be repeated using the Per Protocol Population as a sensitivity analysis with observed data only (i.e. without imputation).

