In addition to the primary analysis, sensitivity analyses will include a best-case analysis, a worst-case analysis, and a complete case analysis (which will include only data from subjects who have IOP measurements at every scheduled follow-up visit).

Poolability of results across centers will be assessed by performing a Cochran-Mantel-Haenszel test comparing the endpoint between the treatment groups stratified by center. The p-value for the Breslow-Day test for homogeneity of odds ratios across centers will be compared to a critical value of 0.15.

The previous analyses will be completed for the following two groups, separately, without the sensitivity analyses and poolability test:

- Subjects who received IOP-reducing intervention; and
- Subjects who did not receive IOP-reducing intervention.

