13.5.3.1 Secondary Safety Analyses

13.5.3.1.1 Incidence of $IOP \geq 30 \text{ mmHg}$

The null hypothesis of no difference between treatment groups in the proportion of subjects with $IOP \geq 30 \text{ mmHg}$ at any follow-up visit will be tested using a chi-square test for the Safety set. A two-sided 95% confidence interval will be constructed around the difference between groups using the normal approximation. If the null hypothesis is rejected then statistical superiority will be claimed for the test OVD in this endpoint.

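### As written, the IOP-spike superiority test (13.5.3.1.1) uses unimputed data with no rule for incomplete eyes, although the primary test of the same endpoint (13.5.1) imputes

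*Combined protocol and SAP*

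**What the plan says.** For the primary safety test, Section 13.5.1 states: "Missing IOP values will be imputed using Markov chain Monte Carlo (MCMC) methods". Twenty datasets are produced, unscheduled readings are then added, and each eye is placed in one of two groups: "This classification will be based on experiencing at least one IOP measurement of 30 mmHg or more at any follow up visit". There is no third group for unknown status. The same section plans a descriptive table of the endpoint on the Safety Population and says of it: "Missing data will not be imputed for this summary table".

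For the superiority test of that endpoint, Section 13.5.3.1.1 says only that it "will be tested using a chi-square test for the Safety set", with a normal-approximation interval for the difference. It mentions neither imputation, nor combining over datasets, nor eyes with a missed visit.

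Section 13.7.1 covers missing data in two sentences. The first is "Imputation of missing primary endpoint data is described in Section 13.3 above"; the second is the default, "Unless otherwise specified in the SAP, missing data will not be imputed".

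The ECD superiority test in Section 13.5.3.2 is different. It is carried out "using the multiple imputation method and statistical model described above for the primary effectiveness analysis".

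For the primary safety analysis, Section 13.5.1 adds that "sensitivity analyses will include a best-case analysis, a worst-case analysis, and a complete case analysis". Nothing similar is listed for the superiority test.

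**The concern.** Two tests of one endpoint would rest on different data. The primary test allows for a spike at an unseen visit; the superiority test, read plainly, does not. The endpoint is the occurrence of at least one high reading, so each missed visit removes a chance to record an event and never adds one. If incomplete eyes without an observed spike are counted as spike-free, the observed rate in each arm is too low. If the arms lose would-be spikes unequally, the difference is biased towards the arm that loses more.

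At stake is a superiority claim on a safety endpoint, which Section 13.2.2.1.1 allows if the null hypothesis is rejected. The analyses that would expose sensitivity to missing IOP are attached only to the primary test.

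**Working it through.** **The text side by side**

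| Test | Section | Missing data |
|---|---|---|
| Spike rate, non-inferiority | 13.5.1 | Imputed, 20 datasets |
| Spike rate, superiority | 13.5.3.1.1 | Not mentioned; 13.7.1 default is none |
| ECD loss, non-inferiority | 13.5.2 | Imputed, 25 datasets |
| ECD loss, superiority | 13.5.3.2 | Primary imputation carried over |

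A single chi-square fits one observed dataset, and the carry-over was written for ECD but not for IOP. Observed data is the plain reading.

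**Inputs from the plan.** Superiority planning rates are 0.117 (test) and 0.256 (control), with 165 per group and one-sided alpha 0.008 (13.3.4). The first Holm step is 0.008333 and the last 0.025 (13.5.3). Allowing for 10% dropout gives 165/(1 − 0.1) ≈ 184 per arm (13.3.3).

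**Assumptions, not in the plan.** A share m of eyes in an arm misses the visit that matters; a share s of spikes is visible only at that visit; incomplete eyes without an observed spike count as spike-free. Then observed rate = true rate × (1 − m·s).

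**Formula.** Probability of declaring the test OVD better = Φ[(d − z·SE0)/SE1], where d is the control rate minus the test rate, SE0 = √(2·p̄(1 − p̄)/n) uses the average rate p̄, and SE1 = √([pt(1 − pt) + pc(1 − pc)]/n).

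**Step 1. Reproduce the stated 80%.** n = 165, alpha 0.008 (z = 2.409): d = 0.139, SE0 = 0.04288, SE1 = 0.04220. Φ[(0.139 − 2.409 × 0.04288)/0.04220] = Φ(0.846) = 80.1%. At 0.008333 it is 80.5%. The stated figure is confirmed.

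**Step 2. Equal missingness, no true difference.** Both rates are multiplied by the same factor, so d = 0 and type I error remains at its nominal level.

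**Step 3. Unequal missingness, no true difference.** True rate 0.117, m = 15% (test) and 5% (control), s = 0.9:
- test: 0.117 × (1 − 0.135) = 0.1012
- control: 0.117 × (1 − 0.045) = 0.1117
- spurious advantage: 0.117 × 0.9 × 0.10 = 0.0105, about 1.1 points

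With n = 184, SE0 and SE1 are both 0.0322. At alpha 0.008333 (z = 2.394), Φ[(0.01053 − 2.394 × 0.03216)/0.03215] = Φ(−2.07) = 0.019. At alpha 0.025 the result is 0.051. If the shares are reversed, so that the control arm misses more, the error falls to 0.003 and 0.011.

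**Step 4. Power with equal missingness.** Eyes counted as spike-free stay in the denominator, so the relevant n is close to 184 rather than 165. At alpha 0.008333, with s from 1.0 down to 0.8:

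| Missed in both arms | n = 165 | n = 184 |
|---|---|---|
| 0% | 80.5% | 85.2% |
| 5% | 77.6–78.2% | 82.6–83.1% |
| 10% | 74.4–75.7% | 79.6–80.8% |

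The n = 165 column charges for missing data twice: once by removing eyes and again by lowering the rates. The n = 184 column is consistent with the classification assumed here.

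**The case against.** The strongest reply is that 13.5.3.1.1 is silent rather than explicit. The first sentence of 13.7.1 speaks of primary endpoint data, not of the primary analysis, and the spike rate is the primary safety endpoint, so the sentence can be read as covering this test. The default also yields to the SAP, to which Section 13 defers further detail, and no separate SAP text is in the document reviewed. This stands as a limit: observed data is the plain reading, not a certainty. It does not remove the point, because the sentence that might settle the question refers to Section 13.3, which is sample size.

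Three stronger readings are tempting and are not supported:
- A reader might infer that the plan counts incomplete eyes as spike-free. The two-group rule in 13.5.1 makes that likely, but it is written for imputed datasets. Exclusion is also possible, as in the complete-case analysis there.
- A reader might infer that the test is underpowered. That depends on holding n at 165 after dropout has already been allowed for.
- A reader might infer that the test is biased in favour of the device. That needs more would-be spikes to be missed in the test arm. The 15% versus 5% split has no basis in the documents, which plan for dropout of up to 10% and mask subjects and postoperative examiners (9.2).

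The consequence is also bounded. The test is reached only if both primary tests and ECD superiority succeed, it is then Holm-adjusted, and unscheduled readings may recover some spikes.

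**Conclusion.** The concern holds in a limited form. On the plain reading, the spike-rate superiority test uses observed data while the primary test of the same endpoint imputes, and the plan gives no rule for an eye with a missed visit and no observed spike. If such eyes are counted as spike-free, both rates are understated. On the assumed 15% versus 5% split with 90% of spikes seen only at the missed visit, the bias is about 1.1 points and one-sided error at the first Holm step rises from 0.008 to 0.019. Those shares are illustrative. With equal missingness, type I error is unaffected and power at 184 per arm is 79.6–80.8% with 10% missed. No stated power or sample-size figure is wrong, and the primary safety conclusion is untouched.

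**What to change.** In Section 13.5.3.1.1, base the superiority test on the imputed datasets from 13.5.1: combine the 20 differences and standard errors as for the primary test, take the one-sided p-value for a difference below zero, and feed it into the Holm procedure. Keep the observed-data chi-square on the Safety set as a sensitivity analysis, and state whether an eye with a missed visit and no observed spike is counted as spike-free or excluded. In Section 13.7.1, correct the cross-reference from 13.3 to 13.5 and say that the imputation covers the superiority test as well.

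The imputed datasets are already produced for the primary test, so the cost is wording and slightly more analysis work on a gated secondary test. The change should be settled before the SAP is approved. If the sponsor prefers observed data for this test, the plan should say so and give the reason for treating it differently from the ECD superiority test.
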